6.7.6 Extension Study Week 36 (Extension Day 252)

The following procedures will be performed at Week 36 of the Extension Study:

- Perform 12-lead ECG;
- Perform symptom-directed physical examination;
- Assess study drug accountability;
- Collect vital signs and anthropometrics;
- Collect blood sample for:
 - Hematology profiles, fasting chemistry profiles, fasting metabolic panel, and fasting lipid parameters (see Appendix C for a full list of analytes to be measured);
 - Total and free (calculated) testosterone, LH, FSH, and estradiol;
 - CK-MB, troponin I, SHBG;
 - PK sampling (pre-dose);
 - ALP isoenzymes;
 - CK-18, FIB-4, and ELF;
 - Type 1 procollagen N-terminal propeptide and CTX;
 - Fibrinogen, haptoglobin, alpha-2 macroglobulin, proBNP, apolipoprotein C-III, and ferritin;
 - APTT, PT, INR;
 - hsCRP;
 - Thyroid axis hormones;
 - Bile acid levels;
- Collect urine sample for pregnancy test (for women of child bearing potential only) and urinalysis;
- Perform DXA scan;
- Provide diet and lifestyle counseling;
- Complete HR-QoL SF-36 assessment;
- Perform Fibroscan (if available);

- Perform MRI-PDFF (within 10 days prior to the visit date while still on treatment); and
- Review alcohol consumption, concomitant medications, and adverse events.

6.7.7 Extension Study Week 38 Follow-up Visit (Extension Day 266)

The following procedures will be performed at the Extension Study Follow-Up Visit (Week 38):

- Collect blood sample for:
 - Hematology, fasting chemistry profiles, and fasting lipid parameters (see Appendix C for a full list of analytes to be measured);
 - CK-MB, troponin I, Total and free (calculated) testosterone, LH, FSH, estradiol, and SHBG;
 - ALP isoenzymes;
 - APTT, PT, INR;
 - Thyroid axis hormones; and
- Review concomitant medications and adverse events.

6.7.8 Extension Study Early Termination Visit

See Section 6.6.

8 PHARMACOKINETIC ASSESSMENTS

8.1 Main Study

Blood samples for PK assessments will be obtained pre-dose from patients at the Baseline Visit (Day 1), Weeks 2, 4, 8, 16, 24, and 36, and the Early Termination Visit. Patients will be instructed not to take study drug prior to PK sampling at these respective study weeks.

At Week 2 visit, PK assessments will be made in the clinic after over-night fast at pre-dose. An 80 mg dose of MGL-3196 or placebo will be administered and PK assessments will be made at 2, 4, 6, and 8 hours post dose. Total $AUC_{0-\infty}$ will be calculated for MGL-3196 and MGL-3196-M1 based on Week 2 $AUC_{(0-8)}$, exposure at 8 h and historic geometric mean elimination rate constant for MGL-3196 and MGL-3196-M1 at the 80 mg dose. Modeling based on historic data obtained for the 80 and 100 mg doses indicate that, using this approach, AUC_{actual} ($AUC_{(0-24)}$) is estimated within 1.8%, SD 5.4% for MGL-3196 given at a dose of 80 mg and is slightly over estimated for MGL-3196-M1 AUC by 5.7% SD 8.5% at a dose of 80 mg. Similar results were obtained for a 100 mg dose. Dose adjustment will be made to 60 mg once per day for any patients whose combined estimated MGL-3196 and MGL-3196-M1 ($AUC_{(0-24)}$) at 2 weeks on the 80 mg dose exceeds 5500 ng*hr/ml. All subjects previously dosed at 50 mg MGL-3196 had combined MGL-3196 plus MGL-3196-M1 less than 5500 ng*hr/ml, geo mean= 3400 ng*hr/ml. Notably, the trough pre-dose drug levels obtained at 50 -100 mg in the MAD study are also predictive of subjects' relative AUCs at a given dose. For patients whose combined estimated $AUC_{(0-24)}$ at 2 weeks at the 80 mg dose is $>11,000$ ng*hr/ml plus SHBG $>150\%$ increased from baseline, the dose will be decreased to 40 mg at the 4 Week visit (or later per Synopsis), because, even given the greater than dose proportionate increase in exposure between a 60 and 80 mg dose, the exposure at 60 mg may be ≥ 5500 ng*hr/ml.

For patients whose combined estimated $AUC_{(0-24)}$ at 2 weeks at the 80 mg dose is ≤ 3000 ng*hr/ml the dose will be increased to 100 mg at the 4 Week visit, as based on a conservative estimates, the predicted exposure at 100 mg will be significantly ≤ 5500 ng*hr/ml. This prediction is based on data obtained in healthy volunteers in which there is greater than dose proportionate increase in MGL-3196 between 80 and 100 mg daily doses, and less than dose proportionate increases in MGL-3196-M1 between 80 and 100 mg doses. Pharmacokinetic data (blinded to patient ID) obtained from the first 21 patients randomized to MGL-3196 suggest that there are no clear differences in MGL-3196 or MGL-3196-M1 exposure at the 80-mg dose between healthy volunteers and NASH patients enrolled in this study.

For the patients who are relatively early in the Main Study (at week 24 or earlier), if their current dose is 100 mg, their Main Study Week 2 predose MGL-3196 PK value < 5 ng/mL and their Main Study Week 2 $AUC \leq 2500$ ng*hr/mL, then their dose will be increased to 120 mg during the Main study and continued on 120 mg if they meet eligibility criteria for the extension study.

8.2 Extension Study

For patients participating in the extension phase of the study, PK assessments will be made at Extension Study Day 1 predose and at the Extension Study Week 2 visit at predose and 4 hours post dose.

All former placebo patients in the Main Study will be randomized to receive 80 mg dose of MGL-3196 for 4 weeks. All patients will have a PK assessment predose and 4 hours postdose at Extension Study Week 2.

Extension Study Dosing Action for Former Main Study Placebo Patients

Extension Study Week 2 MGL-3196 Concentration		Extension Study Week 2 SHBG	Extension Study Week 4 Action
Predose	4 h post dose		
>35 ng/ml	>1350 ng/ml	>125% CFB*	Downtitrate to 40 mg
Patients not meeting criteria for 40, 80, 100 or 120 mg			Downtitrate to 60 mg
<15 ng/ml	< 600 ng/ml	No rule	Remain on 80 mg or increase (see next rows)
<5 ng/ml	≤ 350 ng/ml	No rule	Increase to 100 mg
<2 ng/ml	≤ 150 ng/ml	No rule	Increase to 120 mg

*Change From Baseline, where baseline is Extension Study Day 1

Extension Study Dosing Action for Former Main Study MGL-3196 Treated Patients

Any Main Study patient assigned to MGL-3196 and continuing in the Extension Study will continue on the same dose when starting Extension Study. For patients on 60 or 40 mg, they will continue on the dose unchanged. For patients taking 80 or 100 mg there may be an increase in dose if criteria as described in the table below are met.

Current dose	Main Study Week 2 PK (AUC, combined MGL-3196 plus M1 on 80 mg dose)	Main Study Predose at Week 2	Action in Extension Study
40-60 mg			No change
80 mg	< 3500 ng*hr/ml	< 5 ng/ml	Increase to 100 mg/day
100 mg	≤ 2500 ng*hr/ml	< 5 ng/ml	Increase to 120 mg
120 mg			No change

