3.1.2 Treatment Period

Following randomization, patients will begin the initial 12-week Treatment Period. Patients will undergo liver MRI-PDFF prior to the start of treatment (pre-dose), at the end of the initial 12-week Treatment Period (12 weeks after the start of treatment), and after continuing blinded treatment (MGL-3196 or placebo) for an additional 24 weeks (36 weeks after the start of treatment). A liver biopsy will be obtained prior to start of treatment (pre-dose) if the patient has not had a qualifying liver biopsy within 180 days of randomization and at 36 weeks. During the study, patients will return to the study site periodically for assessment of vital signs (temperature, pulse, respiratory rate, and seated blood pressure), 12-lead electrocardiogram (ECG), and clinical laboratory testing (hematology, chemistry, and urinalysis). During the study, patients who need to be placed on any excluded lipid lowering therapeutics will be discontinued from the study. Blood samples will be collected at specified times for the assessment of lipid parameters, thyroid hormone parameters, and other biomarkers. Patients will be evaluated for adverse events and concomitant medication use throughout the study. Patients should be monitored throughout the study for clinical signs and symptoms of hyper- or hypothyroidism.

A PK assessment will be made at Week 2 including a pre-dose fasting determination and assessments at 2, 4, 6, and 8 hours postdose. As described in PK section, patients who have a calculated $AUC_{inf} \leq 5500 \text{ ng*hr/ml}$ (combined MGL-3196 and MGL-3196-M1) will continue on 80 mg. For patients (~ 10%) with an $AUC_{inf} \leq 3000 \text{ ng*hr/ml}$ as described in Section 8 who are predicted to have exposure at 100 mg that remains $AUC \leq 5550$ based on a conservative calculation, the MGL-3196 dose will be increased from 80 mg to 100 mg at the Week 4 visit. For patients with combined $AUC > 5500 \text{ ng*hr/ml}$, the dose of MGL-3196 will be reduced to 60 mg per day on the Week 4 visit. Patients with $AUC_{inf} > 11,000$ (combined MGL-3196 and M1) plus $SHBG > 150\%$ increase from baseline at Week 2 (indicative that average or steady-state exposure is $> 11,000 \text{ ng*hr/ml}$) will be downtitrated to 40 mg at Week 4. If $SHBG \leq 150\%$, then patient will be downtitrated to 60 mg at Week 4, and patient's Week 4 SHBG and predose concentrations will be evaluated. If at Week 4 $SHBG > 150\%$ increase from baseline and predose

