3.1.3 Extension Study

Within 60 days of completion of the main study Week 36 Visit, patients who meet Inclusion Criteria #9 will be eligible to participate in an extension phase of the study for an additional 36 weeks of treatment. The extension study will initially be blinded to treatment group, but the extension study will become unblinded at the time of completion of the main study. At the extension study initiation which may be as early as the 38-week visit, (Extension study Day 1 visit), patients on placebo in the main study will begin receiving 80 mg MGL-3196 and at the Week 2 visit, all patients will have a PK assessment, and at Week 4 any dose adjustments will be made. All patients on active drug in the main study will initially receive MGL-3196 at the dose they were assigned to at the completion of the main study, and at the Week 4 visit they may have their dose adjusted up or down based on the Week 2 PK.

Dose Adjustments in Main or Extension Study in Patients Assigned to MGL-3196 in Main Study

Current dose	Main Study Week 2 PK (AUC, combined MGL-3196 plus M1 on 80 mg dose)	Main Study Predose at Week 2	Main study Predose Week 8 (post dose adjustment)	Main Study SHBG <+75% CFB at Week 12 (post dose adjustment)	Action in Main and/or Extension Study
40 mg			< 5 ng/ml	Yes	Increase to 60 mg/day
60 mg	<5500 ng*hr/ml ¹		< 1 ng/ml	Yes	Increase to 80 mg/day
80 mg	<4000 ng*hr/ml AND SHBG %CFB<90)			OR ² Yes	Increase to 100 mg/day
100 mg	≤3000 ng*hr/ml	<5 ng/ml			Increase to 120 mg
120 mg					No change

¹ Recalculated 80 mg AUC based on corrected elimination rate constant for MGL-3196 and M1 in patients who demonstrated average predose levels <5 ng/ml at Week 2,4,8 and had initial calculated AUC<7000 ng*hr/ml. Change from Baseline (CFB).

² Either exposure <4000ng*hr/ml with SHBG%CFB<+90 OR SHBG<+70%CFB qualifies for increase to 100 mg.

Dose Adjustments in the Extension Study in Patients Assigned to Placebo in the Main Study

Extension Study Week 2 MGL-3196 Concentration		Extension Study Week 2 SHBG	Extension Study Week 4 Action
Predose	4 h post dose		
>35 ng/ml	>1350 ng/ml	>200% CFB*	Downtitrate to 40 mg
Patients not meeting criteria for 40, 80, 100 or 120 mg			Downtitrate to 60 mg
<15 ng/ml	<600 ng/ml	OR <75% CFB increase**	Remain on 80 mg or increase (see next rows)
<5 ng/ml	≤ 350 ng/ml	No rule	Increase to 100 mg
<2 ng/ml	≤ 150 ng/ml	No rule	Increase to 120 mg

*Change From Baseline, where baseline is Extension Study Day 1.

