**Either predose<15ng/ml plus 4h<600ng/ml OR SHBG<+75%CFB.

No titrations will be made based on TSH which has not changed in the Main Study. TSH will be unblinded in the Extension Study. Downtitrations have not been needed for changes in FT4, but the same downtitration rules will apply in the Extension Study.

At the Extension Study Week 12 Visit, patients will have an MRI-PDFF. Within 10 days prior to or at the Extension Study Week 36 visit while the patient is still on treatment another MRI-PDFF will be performed. If available, a fibroscan may be performed at the Extension Study Week 36 visit.

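### Protocol Sections 8.2 and 3.1.3 give different extension dose rules, so patients between the two sets of cut-offs are prescribed different doses depending on the section read

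*Protocol*

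**What the plan says.** Section 5.1 of the protocol sends the reader to Section 8.2 for the Week 4 extension dose adjustment of patients previously on MGL-3196. Section 8.2 says of them: "For patients on 60 or 40 mg, they will continue on the dose unchanged". Its tables then set the steps from 80 to 100 mg and from 100 to 120 mg, and the steps for former placebo patients.

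Section 3.1.3 covers the same decisions with other rules, and the Synopsis tables agree with it. For former MGL-3196 patients its text says that "they may have their dose adjusted up or down based on the Week 2 PK". Its table has a 40 mg row ending in "Increase to 60 mg/day". A 60 mg row leads to 80 mg, using an AUC recalculated "in patients who demonstrated average predose levels <5 ng/ml at Week 2,4,8 and had initial calculated AUC<7000 ng*hr/ml". For 80 mg, a footnote adds a route on SHBG alone: "OR SHBG<+70%CFB qualifies for increase to 100 mg". For former placebo patients, a footnote gives the condition for staying on 80 mg: "Either predose<15ng/ml plus 4h<600ng/ml OR SHBG<+75%CFB".

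The 3.1.3 table for former MGL-3196 patients is headed as applying to the main study as well. Section 8.1 has its own main-study 120 mg step. For patients on 100 mg at Week 24 or earlier, with Week 2 predose below 5 ng/ml and AUC at or below 2500 ng*hr/ml, "then their dose will be increased to 120 mg during the Main study and continued on 120 mg".

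**The concern.** The amendment summaries show where each set came from: 8.2 matches the Amendment 5 tables, and 3.1.3 and the Synopsis match those of Amendment 6. The conflict is not between the log and the body, however. Both sets stand in current body text.

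The cross-references do not settle which one governs. Section 5.1 points to the older rules. Section 5.5.3, which ties the response system's drug assignment to the protocol, points to 3.1.2, which has no extension table and no 120 mg step. The Synopsis PK paragraph points to page 35, which by the table of contents is the Amendment 1 summary; the Synopsis starts on page 37.

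At stake are the dose that an individual extension patient receives and whether a given dose change complies with the protocol or deviates from it. SAP 2.2.1 says that some former MGL-3196 patients had an increase specified in advance, but does not say under which rule.

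**Working it through.** There is no planned figure to reproduce. The check sets the two rule sets side by side and passes the same patients through both. AUC is the combined main-study Week 2 value on 80 mg (ng*hr/ml), concentrations are in ng/ml, and SHBG is percent change from baseline.

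| Decision | Section 8.2 | Section 3.1.3 and Synopsis |
|---|---|---|
| Former MGL-3196, on 40 mg | No change | 60 mg if Week 8 predose <5 and Week 12 SHBG <+75% |
| On 60 mg | No change | 80 mg if recalculated AUC <5500, Week 8 predose <1 and SHBG <+75% |
| On 80 mg | 100 mg if AUC <3500 and Week 2 predose <5 | 100 mg if AUC <4000 with SHBG <+90%, or on low SHBG alone (<+75% in the column header, <+70% in footnote 2) |
| On 100 mg | 120 mg if AUC ≤2500 and Week 2 predose <5 | 120 mg if AUC ≤3000 and Week 2 predose <5 |
| Former placebo, to 40 mg | Predose >35, 4 h >1350, SHBG >125% | Predose >35, 4 h >1350, SHBG >200% |
| Former placebo, stay on 80 mg | Predose <15 and 4 h <600 | The same, or SHBG <+75% alone |

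Illustrative patients follow. Their values are assumptions chosen to fall between the cut-offs, and conditions within a row are read as all required unless the table says OR.

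| Patient | Dose by 3.1.3 | Dose by 8.2 |
|---|---|---|
| 1. On 40 mg, Week 8 predose 4, SHBG +60% | 60 | 40 |
| 2. On 60 mg, initial AUC 6500, predose 3, 2 and below 1 at Weeks 2, 4 and 8, recalculated AUC 5200, SHBG +60% | 80 | 60 |
| 3. On 80 mg, AUC 3800, predose 8, SHBG +80% | 100 | 80 |
| 4. On 80 mg, AUC 4200, predose 6, SHBG +60% | 100 | 80 |
| 5. On 80 mg, AUC 3300, predose 3, SHBG +100% | 80 | 100 |
| 6. On 100 mg, AUC 2800, predose 3 | 120 | 100 |
| 7. Former placebo, predose 40, 4 h 1400, SHBG +150% | 60 | 40 |
| 8. Former placebo, predose 20, 4 h 800, SHBG +60% | 80 | 60 |

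Notes on single rows:

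- **Patient 2.** SAP 3.9 gives a quantification limit of 1 ng/ml, so a Week 8 value that meets the criterion is one below that limit. The mean predose is then at most (3 + 2 + 1)/3 = 2.0, under the footnote's 5. The recalculated AUC is assumed, because the corrected rate constant is not given.
- **Patient 5** goes the other way: 8.2 raises the dose and 3.1.3 does not. It needs AUC above 3000 and below 3500, predose below 5 and SHBG at or above +90%. At AUC 3000 or less, Section 3.1.2 already says "the MGL-3196 dose will be increased from 80 mg to 100 mg at the Week 4 visit".
- **Patient 6.** Anyone raised to 100 mg at Week 4 has AUC at or below 3000. For that patient the 3.1.3 AUC condition is always met and only predose decides, while 8.2 still leaves out AUC above 2500. In the main study, 8.1 provides the step only at 2500 or below and up to Week 24; 3.1.3 sets 3000 and no week limit.

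None of the eight results depends on whether the SHBG-alone limit is 70% or 75%. A ninth patient does: on 80 mg with AUC 4200 and SHBG +72%, the header gives 100 mg and the footnote 80 mg, both within 3.1.3.

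The two sets agree for patients on 120 mg, for patients on 100 mg with AUC at or below 2500 and predose below 5, and in the 100 and 120 mg rows of the former-placebo table.

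Rough scale: the Amendment 5 rationale expects about 25% of 125 patients to be eligible for the extension, 0.25 × 125 ≈ 31. Section 3.1.2 puts about 10% in the Week 4 step to 100 mg; with the 84 active patients in the Amendment 6 safety table, 0.10 × 84 ≈ 8. Neither figure counts patients inside a conflict band.

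**The case against.** The strongest reply is that a careful reader can tell which set is newer. The Synopsis and 3.1.3 agree, 8.1 itself defers to the Synopsis on one dosing detail, and the Amendment 6 rationale calls its Table 3 levels the main basis for extension dosing. That rationale also allows minor changes to the algorithms. Unblinded personnel make the adjustments, and the extension is open label and exploratory.

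Much of this stands and limits the harm. It does not settle the rule. The Amendment 6 wording concerns Table 3 only and sits in the rationale, while the body text of 5.1 still points to 8.2. Nor is the newer set consistent in itself, as the ninth patient shows. The same rationale says that the 80 mg SHBG rule is the only change to Table 3, yet the 40 mg SHBG cut-off also differs between 8.2 and 3.1.3, so that value needs confirming.

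The case against stronger readings also holds:

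- A reader might infer that the extension's dose-exposure results cannot be interpreted. The documents do not support this. Such analyses use the dose taken and the exposure measured, and SAP 2.2.1 reports a later move of all extension patients to at least 80 mg that appears in neither table.
- A reader might infer that 8.1 forbids 120 mg above AUC 2500. It says who will be increased and is silent on the others, so it is narrower than 3.1.3 and not a prohibition.
- A reader might take 31 and 8 as upper limits. They are estimates, and Amendment 6 widens eligibility by a few patients.

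**Conclusion.** The concern holds for extension patients between the cut-offs, not for every extension patient. For them the protocol prescribes two doses, 20 mg apart in each worked case, and neither section is uniformly the more cautious. Section 5.1 points to 8.2 only for former MGL-3196 patients; the former-placebo conflict arises because 8.2 also carries its own table for them.

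The consequence is limited to individual extension dosing and the classification of deviations, plus the narrower 120 mg criterion in 8.1 for some main-study patients on 100 mg. How many patients were affected is unknown and may be few. SAP 2.2.1 lists no 40 mg step among former placebo outcomes, so it gives no sign that the 125% versus 200% difference put anyone on 40 mg. The later move to at least 80 mg means that the 40 and 60 mg differences did not last. The Week 12 primary analysis compares pooled active treatment with placebo and does not use these rules.

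The point should be fixed because it concerns a decision threshold and costs little to correct. The conclusion rests on reading the table conditions as joint where no OR appears, and on illustrative patient values.

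**What to change.** - **Section 8.2:** delete both dosing tables and the sentence leaving 40 and 60 mg patients on their dose, and state that extension dose adjustments follow the tables in Section 3.1.3.
- **Section 8.1, last paragraph:** align the 120 mg criterion with 3.1.3 (AUC at or below 3000) and state whether the Week 24 limit stays.
- **Cross-references:** change 5.1 to cite 3.1.3, and 5.5.3 to cite 3.1.2 and 3.1.3.
- **Synopsis:** replace the page 35 reference by Section 3.1.3, and raise the upper dose in the dosage paragraph from 100 to 120 mg.
- **Section 3.1.3:** have the clinical team confirm 125% or 200% SHBG for the former-placebo step to 40 mg, and 70% or 75% for 80 to 100 mg. Reconcile the text allowing adjustment down on Week 2 PK with a table for former MGL-3196 patients that has no down step.

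The cost is a protocol clarification or amendment with two clinical confirmations. It needs no new procedures, visits or patients.

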9 SAFETY ASSESSMENTS

9.1 Adverse Events

An adverse event is defined as any untoward medical occurrence in a clinical investigation patient administered a pharmaceutical product, which does not necessarily have a causal relationship with this treatment. An adverse event can therefore be any unfavorable and/or unintended sign (including an abnormal laboratory finding), symptom, or disease temporally associated with the use of an investigational medicinal product, whether or not related to the investigational medicinal product. All adverse events, including observed or volunteered problems, complaints, or symptoms, are to be recorded on the appropriate eCRF.

Adverse events, which include clinical laboratory test variables, will be monitored and documented from the time of informed consent until study participation is complete. Patients should be instructed to report any adverse event that they experience to the Investigator. Beginning at the Screening Visit, investigators should make an assessment for adverse events at each visit and record the event on the appropriate adverse event eCRF.

Wherever possible, a specific disease or syndrome rather than individual associated signs and symptoms should be identified by the Investigator and recorded on the eCRF. However, if an observed or reported sign or symptom is not considered a component of a specific disease or syndrome by the Investigator, it should be recorded as a separate adverse event on the eCRF. Additionally, the condition that led to a medical or surgical procedure (eg, surgery, endoscopy, tooth extraction, or transfusion) should be recorded as an adverse event, not the procedure.

Any medical condition already present at screening should not be reported as an adverse event unless the medical condition or signs or symptoms present at baseline change in severity or seriousness at any time during the study. In this case, it should be reported as an adverse event.

Clinically significant abnormal laboratory or other examination (eg, ECG) findings that are detected during the study or are present at screening and significantly worsen during the study should be reported as adverse events. The Investigator will exercise his or her medical and scientific judgment in deciding whether an abnormal laboratory finding or other abnormal assessment is clinically significant. Clinically significant abnormal laboratory values occurring during the clinical study will be followed until repeat tests return to normal, stabilize, or are no longer clinically significant. Any abnormal test that is determined to be an error does not require reporting as an adverse event.

